## 5.0 Study Design\*

5.1 Describe and explain the study design (e.g. case-control, cross-sectional, ethnographic, experimental, interventional, longitudinal, observational).

Response:

This study has an experimental design. Participants will be randomly assigned to 1 of 2 interventions or a control group in which they will shop in-person as usual. Stratification factors will be sex and diabetes status: type 2 diabetic vs. at risk for type 2 diabetes, defined as a diagnosis of prediabetes or meeting criteria for increased risk of developing type 2 diabetes as determined by the American Diabetes Association Type 2 Diabetes Risk Test. In all groups, recipe cards that follow the evidence-based DASH diet and correspond to dietary recommendations for diabetic patients will be provided. The *Online* intervention will utilize online grocery shopping (shopping at a local grocery store via Instacart) to promote healthier purchasing, removing visceral factors that can lead to impulse purchases in stores. The *Defaults* intervention will augment this intervention, showing participants a default cart when they log into their accounts. They will be told that their cart has been filled with items that conform to a diet appropriate for diabetes prevention, management, and overall health and can be used to make the recipes from the provided recipe cards, and that they may modify it as they like.

At baseline, all participants will complete a survey online or via phone and then will grocery shop in-person as usual. Participants will then be randomized and receive further instructions. For the next 3 weeks, they will receive recipe cards and shop in accordance with their assigned study group. The following week (post), they will shop using the method of their choice (in-person, online) and complete a survey again. Household receipt data will be collected throughout the study. The baseline period will also serve as a run-in period, and participants who do not comply with study guidelines for baseline procedures (including guidelines for receipt submission) will not be randomized for further participation. Primary analyses will examine intervention effects on grocery purchases, with additional analyses on spending and dietary intake. All participant interactions will occur online or via phone.

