## 12.0 Procedures Involved\*

12.1 *Provide a description of **all research procedures or activities** being performed and when they are performed once a subject is screened and determined to be eligible. Provide as much detail as possible.*

*NOTE: This should serve as a blueprint for your study and include enough detail so that another investigator could pick up your protocol and replicate the research. For studies that have multiple or complex visits or procedures, consider the addition of a schedule of events table in in your response.*

Response:

The proposed study will occur during 2019-2020 with data collection occurring for about 17 months. Recruitment and data collection will occur on a rolling basis, with individual participants' involvement being for about 6 weeks. All data will be collected online or via phone.

Following completion of initial screening, participants will complete consent procedures and a HIPAA form for their physician to confirm their diabetes/prediabetes diagnosis, or specific health characteristics that increase their risk of developing type 2 diabetes in accordance with the American Diabetes Association Type 2 Diabetes Risk Test [see Consent and HIPAA form]. Physicians will be contacted using their modality of choice; this may include phone, email, fax via efax.com, or in-person communication). Participants will be mailed their Clincard for participant payment and move on to baseline procedures: a questionnaire [See attachment: Questionnaires], a baseline shopping trip and receipt submission, and a brief phone interview with questions about their shopping trip [See attachment: Phone interview]. Any participant who does not follow guidelines for baseline procedures will not proceed to randomization (but will be compensated for their time, as detailed below).

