Participants' baseline shopping trips will be in-person at their usual grocery store. Following their baseline shopping trip, participants will submit a photograph of their household receipts via email and of a receipt information form (attached). Study staff will contact participants to remind them about this if photographs are not received within the time frame discussed during consent procedures. When the photos are received, study staff will mail participants their Clincards to be used for participant payments and will contact participants via phone to ask follow-up questions and share with participants their assigned study group [See attachment: Phone interview].

Participants will be randomized in blocks to the *Online*, *Defaults*, or *Control* group, stratifying by diabetes status (diabetes vs. increased risk for developing type 2 diabetes). Study staff will consult a pre-populated spreadsheet in order to determine the study group of each participant. Participants in the *Online* and *Defaults* groups will receive instructions on how to access an online grocery shopping account on Instacart ([www.instacart.com](http://www.instacart.com)). Instacart is a platform through which customers can grocery shop online and have their groceries delivered within a designated window. Many leading grocery retailers offer grocery shopping via Instacart, including Tops and Wegmans, both of which are based in Western New York; there are approximately 250 locations of these chains throughout the Northeastern United States, including but not limited to: New York, New Jersey, Pennsylvania, and Massachusetts.

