## **22.0 Withdrawal of Subjects\***

☐ N/A: This study is not enrolling subjects. This section does not apply.

*22.1 Describe **anticipated** circumstances under which subjects may be withdrawn from the research without their consent.*

Response:

Participants who do not comply with study guidelines at baseline (including guidelines for receipt submission) will not be randomized for further participation and withdrawn from the research. Participants also have the ability to stop participating at any time if they so choose.

22.2 *Describe any procedures for orderly termination.*

*NOTE: Examples may include return of study drug, exit interview with clinician. Include whether additional follow up is recommended for safety reasons for physical or emotional health.*

Response:

Participants will be debriefed about the nature of the study and the reason for their removal.

22.3 *Describe procedures that will be followed when subjects withdraw from the research, including retention of already collected data, and partial withdrawal from procedures with continued data collection, as applicable.*

Response:

Participants can withdraw from the research at any time. If participants withdraw, no further data will be collected, but any information that had been provided may be retained and analyzed.

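### Section 12.1 describes no allocation concealment: staff read the arm from a pre-filled spreadsheet and share it in the baseline interview call, with no rule that run-in compliance is recorded first

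*Combined protocol and SAP*

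**What the plan says.** Section 12.1 lists the baseline procedures as a questionnaire, a shopping trip with receipts sent in, and "a brief phone interview with questions about their shopping trip". It then sets the run-in rule: "Any participant who does not follow guidelines for baseline procedures will not proceed to randomization". Section 22.1 repeats the rule and names one guideline: "Participants who do not comply with study guidelines at baseline (including guidelines for receipt submission) will not be randomized".

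Once the receipt photographs arrive, Section 12.1 says that staff "will contact participants via phone to ask follow-up questions and share with participants their assigned study group". Allocation is in blocks, with strata, and the arm is obtained this way: "Study staff will consult a pre-populated spreadsheet in order to determine the study group of each participant".

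Section 5.1 gives the intended order. It describes the baseline survey and shopping trip and continues: "Participants will then be randomized and receive further instructions".

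**The concern.** Randomisation protects the comparison only if the decision to let someone in is made without knowledge of the arm. Here the sequence already exists as a filled-in list, so randomising a participant amounts to looking up a row. The people who look it up are study staff. The run-in exclusion rests on guidelines whose pass criteria are not set out, apart from the mention of receipt submission, and the protocol does not say who decides or when. If a caller knows the arm while a borderline participant is still being judged, leniency can differ between arms.

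This matters because the primary comparison in Section 19.1 is between groups at post-test, so selective entry could carry straight into it. The arms also differ in staff work and cost. The Online and Defaults groups need accounts, and the Defaults group needs carts filled (Section 12.1). Both online groups also receive reimbursement, which is $53.73 and $103.47 per participant in the two examples of Section 27.1. Uneven leniency is therefore plausible, although nothing shows that it occurred.

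**Working it through.** The plan gives no figure to reproduce, so the check is mainly a reading of the text.

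1. **Is the phone interview a baseline procedure?** Yes. Section 12.1 lists it last among them.

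2. **Can failing it bar randomisation?** Under the rule in Section 12.1, yes: the rule covers baseline procedures in general. Section 22.1 mentions receipt submission as something included, so receipts are an example and not the whole list.

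3. **Is the interview call the call that discloses the arm?** As written, yes. The interview and the call that shares the group both point to the same phone interview attachment, and the call is placed after the receipts come in.

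4. **When must staff hold the assignment?** At the latest, when they share it in that call. Two sequences fit the text:
   - (a) interview, compliance decision, look-up, disclosure;
   - (b) look-up, interview, compliance decision, disclosure.

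   Sections 1.0 and 5.1 point to (a). No sentence excludes (b), because no step makes the look-up wait for a recorded decision.

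5. **Is concealment described anywhere?** No. Sections 18.1 and 20.1 give password protection and restricted access to the file that links names to study numbers. They describe access to study data in general for the investigator and research staff. Neither section says anything about the allocation list.

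6. **Would hiding the list be enough on its own?** Not if blocks are small and fixed. Callers disclose each assignment, so they know the past ones. Block size and allocation ratio are not given. As an illustration, assume 1:1:1 blocks of 3, 6 or 9 within a stratum and a caller who knows only the past assignments and the block size.
   - Share of assignments known with certainty:
     - block of 3: 1/3 = 33%;
     - block of 6: (1 + 1/5)/6 = 20%;
     - block of 9: (1 + 2/8 + 2/8 × 1/7)/9 = 14%.
   - Share guessed correctly by naming an arm with most places left:
     - block of 3: (1/3 + 1/2 + 1)/3 = 61%;
     - blocks of 6 and 9, by simulation: 56% and 53%.
   - By chance the share guessed correctly would be 33%.

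   A caller who could see the whole list would know 100%.

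7. **Can the resulting bias be sized?** No. It depends on how many run-in participants are borderline, how their purchases differ from the rest, and how often they are handled differently by arm. The documents give none of these.

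**The case against.** The best defence is that the protocol puts baseline before randomisation, and that Section 12.1 mentions the follow-up questions before the sharing of the group. Receipt submission, the only guideline named, is met before the call is placed. The questionnaire and shopping trip are also listed ahead of the interview. What remains is a brief interview that a participant completes by answering, so there may be little left to judge. The phone script and receipt instructions are attachments not available here and may fix the order of steps. Section 8.4 also refers to the pilot nature of the study.

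Much of this stands, and it rules out some stronger readings. A reader might infer that the spreadsheet is open to all staff, that later rows are visible, or that compliance is decided on the call. The text says none of these things. A reader might also infer that baseline purchase data could be coloured by knowledge of the arm. That is not supported: nutrients and food groups come from receipts (Section 12.2), and the baseline receipts are sent before the call.

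The defence does not supply a safeguard. An intended order is not a lock when the sequence already exists, and the run-in criteria are left undefined. Pilot or not, the trial tests between-group hypotheses (Sections 2.2 and 19.1).

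**Conclusion.** The point holds in a limited form. The protocol states an allocation method in which study staff look up a pre-filled list. It describes no concealment and does not require the run-in decision to be recorded before the look-up. Arm-dependent exclusion is therefore possible; it is not documented. It would go too far to say that allocation was unconcealed: the accurate statement is that no concealment is described.

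No bias figure should be attached to this. The predictability figures under working show only how well a caller could foresee the next arm under assumed block sizes; they do not measure bias. The conclusion rests on reading the two mentions of the phone interview in Section 12.1 as one call, and on the unseen attachments not already imposing a lock. This is a change worth making because it is cheap, not a flaw that invalidates the design.

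**What to change.** In Section 12.1:

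- Complete the baseline interview, then log a dated, locked run-in pass or fail against stated criteria. Section 19.2 counts an unconfirmed diagnosis as a run-in loss, while Section 10.1 lets participants proceed before confirmation, so the criteria should say whether confirmation is part of the pass.
- Only then release one assignment at a time from a list that calling staff cannot open. It could be a password-protected list held by a team member who does not make the calls, or a randomisation module if the existing software supports stratified blocks.
- Do not disclose block sizes to callers.
- Report run-in exclusions with reasons and dates.

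Whoever builds the list also needs the strata reconciled: Section 5.1 gives sex and diabetes status, Section 12.1 diabetes status only. If enrolment is already over, state who held the list and who could open it, and report the exclusions as above.

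The cost is a few sentences and a hidden list. With at most 100 enrolled (Section 7.1) over about 17 months of data collection (Section 12.1), there are at most 100/17, or about 6, releases a month, so no extra staff should be needed. The downside is a short delay, or a second brief contact, before participants learn their group.

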## 12.2 Describe what data will be collected.

*NOTE: For studies with multiple data collection points or long-term follow up, consider the addition of a schedule or table in your response.*

Response:

### Data to be collected include:

- \*Confirmation of diabetes status or diabetes risk status (see attachments: Consent and HIPAA Form)
- \*Demographic questions collected at baseline (see attachment: Questionnaires)
- \*Changes in daily routine, perceived stress and loneliness questions at baseline (see attachment: Questionnaires)
- \*Calories, carbohydrates, sugar (total sugar and/or added sugar), and food groups each week of the 5-week shopping period, from receipts (see additional details below)
- \*Information on which purchased items will be consumed by the participant and information about foods acquired from other sources besides the target grocery store that week (administered after each shopping trip, see attachment: Phone interview)
- \*Dollars spent on groceries at each time point, from receipts (each week)
- \*Dietary intake from a Food Frequency Questionnaire (see details below and attachment: Questionnaires; collected at post-test)
- \*Exit questionnaire (completed at the end of the study; see attachment: Questionnaires)

### Additional details:

Calories, carbohydrates, sugar (total sugar and/or added sugar), and food groups will be generated from each of the five weeks of receipt data using Nutritionist Pro software. Each item on the receipt, as well as the item quantity and weight, will be entered into the software following procedures from Hollis-Hansen et al. (Hollis-Hansen, Seidman, O'Donnell, & Epstein, 2018). Standard values from the USDA will be entered in the case of any missing information as done previously. Nutritional quality will be examined using the DASH diet scores based on the amount of 8 food types encouraged or discouraged by the DASH diet (e.g., fruits,

vegetables, sweetened beverages). Methods previously used to calculate DASH diet scores from intake data will be adapted for use in this context.

The food frequency questionnaire is used to calculate nutrient intake. It is a structured self-administered questionnaire with pre-specified response options.

12.3 List any instruments or measurement tools used to collect data (e.g. questionnaire, interview guide, validated instrument, data collection form).

*Include copies of these documents with your submission.*

Response:

- Baseline demographic questionnaire – (see attachment: Questionnaires)
- Food frequency questionnaire (to be completed at post-test) – (see attachment: Questionnaires)
- Food receipt collection instructions (see attachment: Receipt collection)
- Food receipt form (see attachment: Receipt collection)
- Exit survey – (see attachment: Questionnaires)
- Consent and HIPAA form

12.4 Describe any source records that will be used to collect data about subjects (e.g. school records, electronic medical records).

Response:

N/A, no source records will be used to collect data about subjects.

12.5 Indicate whether or not **individual** subject results, such as results of investigational diagnostic tests, genetic tests, or incidental findings will be shared with subjects or others (e.g., the subject's primary care physician) and if so, describe how these will be shared.

Response:

N/A, no individual subject results will be shared with subjects or others.

12.6 Indicate whether or not **study** results will be shared with subjects or others, and if so, describe how these will be shared.

Response:

No, study results will not be shared with subjects or others besides publication of study results in scientific journals and accompanying write-ups (e.g., conference presentations, press releases to promote published articles). All such publications will feature data in aggregate and no identifying information.

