Accounts will be set up for the participants by study staff, with shared access. Participants will enter their credit/debit card information and purchase their own groceries, to enhance ecological validity. Only the last 4 digits of the participant's credit or debit card number will be visible to study staff when accessing the account to download receipt data (*Online* and *Defaults* groups) and populate the default cart (*Defaults* group). During the 3 weeks that follow randomization, *Control* group participants will be asked to shop as they normally would, in-person at Tops or Wegmans. Those in *Online* and *Defaults* groups will be asked to shop as they normally would but using their grocery store's Instacart platform. In addition, the *Defaults* group will be told that their cart will be pre-filled with items that conform to a diet appropriate for diabetes management, prevention, and overall health. The items will correspond to the DASH diet. All participants will receive 3 DASH-diet friendly recipe cards each week, and the items in the *Defaults* group's carts will correspond to the recipes. The default cart will be populated by study staff after study group assignment and will be re-populated to prepare for the next purchase each time the participant completes a shopping trip. During the post-test week, all participants will be asked to shop using the method of their choice (in-person, online); no default carts or recipe cards will be given. At post-test participants will also complete a Food Frequency Questionnaire as well as an Exit Questionnaire (see attachment: Questionnaires).

Based on inclusion criteria, we expect each participant to shop at least once during each of the three intervention weeks; participants can shop more than once per week if this is what they typically do. Either way, they will be instructed to continue to submit their receipts from all household grocery shopping at

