the prior study's intermediary group (incentives; Cohen's  $d=0.44$ ) to conduct a more conservative sample size calculation, given our interest in detecting effects on purchasing between our intermediary group (*Online*) and the other groups. This calculation yielded a sample size of 54. We increased this to account for participants lost during the run-in period (i.e. failure to confirm diabetes diagnosis, failure to complete baseline procedures) as well as participants lost due to attrition, with a plan to enroll up to 100 participants.

*19.3 Describe any procedures that will be used for quality control of collected data.*

Response:

Some data will be entered directly by participants (online questionnaires). All other study data will be entered by trained staff: study staff will enter participant responses into online forms while phone screening/phone interviews are completed. Study staff will also enter information from receipts into NutritionistPro (e.g., nutrition information) and Microsoft Excel (e.g., dollars spent) for analysis of study aims. Entered data will be double entered and/or checked for quality control.

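### Receipt coding is not masked to arm and USDA substitutions are not recorded, so differential coding error between Control and the online arms cannot be excluded, chiefly in the intervention weeks

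*Combined protocol and SAP*

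**What the plan says.** Section 12.2 (additional details) sets the unit of coding: "Each item on the receipt, as well as the item quantity and weight, will be entered into the software following procedures from" a cited earlier study. Where something is lacking, "Standard values from the USDA will be entered in the case of any missing information as done previously". The section does not define what counts as missing and does not ask for a record of which items were filled in this way.

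Section 19.3 says who does the work: "Study staff will also enter information from receipts into NutritionistPro". The check is that "Entered data will be double entered and/or checked for quality control". Neither section mentions masking.

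Section 12.1 shows what study staff know. "Study staff will consult a pre-populated spreadsheet in order to determine the study group of each participant", they tell participants their group by phone, and "The default cart will be populated by study staff after study group assignment". They can also open the Instacart accounts of the two online arms to download receipts.

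Section 12.1 also fixes how people shop. In the three intervention weeks the Control "group participants will be asked to shop as they normally would, in-person at Tops or Wegmans". Online and Defaults are to shop normally "but using their grocery store's Instacart platform". At post-test every arm may choose its mode. Section 19.1 places the primary comparisons at post-test and adds overall and change-by-group comparisons. Section 3.0 counts purchases over the whole study period among the primary analyses.

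**The concern.** Calories, carbohydrates and sugar depend on a person deciding which product a receipt line is, what size it is and, where that is unclear, which standard value to use. Two routes could make this differ by arm.

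The first is receipt type. If in-store and Instacart receipts leave different gaps, or are resolved from different sources, the same product can get different nutrient values. In the intervention weeks receipt type follows the Control versus online split by design. Such error does not average out with more participants.

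The second is coder expectation. The hypotheses in Section 2.2 have a direction (Defaults lowest in calories, carbohydrates and sugar, Online in between), and an unmasked coder may lean that way in any week.

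Because substitutions are not recorded, the team could not show afterwards that they were balanced across arms.

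**Working it through.** **Step 1. Which contrasts are exposed.** Setting Sections 12.1, 19.1 and 3.0 side by side gives:

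| Contrast | Receipt-type route | Coder expectation |
|---|---|---|
| Control vs Online or Defaults, intervention weeks | open by design | open |
| Online vs Defaults, intervention weeks | closed (same receipt type) | open |
| Overall and change contrasts with Control | open through the intervention weeks | open |
| Any pair of arms at post-test | open only as far as arm changes the chosen mode | open |

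**Step 2. Which outcomes are exposed.** Calories, carbohydrates and sugar use the nutrient values directly. The DASH score in Section 12.2 rests on amounts of 8 food types. A substituted nutrient value does not enter it, so it is affected only through item classification, size or weight.

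**Step 3. The plan's own figures.** The plan gives no rate of missing item information, overall or by receipt type, so there is no figure for coding error to reproduce. Its sample sizes serve here only to set a number per arm. A three-group interaction test with an assumed two time points and correlation 0.5 gives both of them as totals, using f = d/2 and λ = f² × N × 2/(1 − 0.5):
- d = 0.96: f = 0.48, N = 15, λ = 0.48² × 15 × 4 = 13.82, power 0.840.
- d = 0.44: f = 0.22, N = 54, λ = 0.22² × 54 × 4 = 10.45, power 0.809.

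That means 54/3 = 18 per arm, and at most 100/3, about 33, at full enrolment.

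**Step 4. Illustration of size. Every input is an assumption.** Let g be the extra share of items lacking information on one receipt type, e the systematic error of standard values in one direction, and CV the coefficient of variation of the weekly total. Treat share of items as share of the nutrient total. With 100% online in one arm and 0% in the other:

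shift in SD = g × e / CV

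- g = 0 or e = 0: shift 0.
- g = 0.10, e = 0.10, CV = 0.6: 0.01/0.6 = 0.017 SD.
- g = 0.30, e = 0.30, CV = 0.4: 0.09/0.4 = 0.225 SD.

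**Step 5. Carry-over to post-test.** Multiply by the difference between arms in the share shopping online, also assumed. The top value becomes:
- shares 70% vs 20%: 0.225 × 0.50 = 0.11 SD.
- shares 50% vs 30%: 0.225 × 0.20 = 0.045 SD.
- equal shares: 0.

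Against the planning effect of 0.44 these are about 26%, 10% and 0%.

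**Step 6. Consequence for a single two-arm comparison.** With no true effect and a two-sided 5% t-test, the rejection rate is:

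| Shift | 18 per arm | 33 per arm |
|---|---|---|
| 0 | 5% | 5% |
| 0.1 SD | 6.0% | 6.9% |
| 0.2 SD | 9.0% | 12.6% |

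**The case against.** The strongest reply is that the mechanism is undocumented and largely misses the main comparison. No section says that gaps differ between in-store and Instacart receipts. The substitution rule makes no distinction by arm. Participants send a receipt information form with their photographs, which the revision history says was added so that they could explain the items. Section 12.1 collects Instacart receipts from participants too, for consistency. Entries are double entered and/or checked. The detailed coding procedure is cited rather than reproduced, and the study calls itself a pilot.

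Most of this stands as a limit on size. The revision history for version 11 adds another: wording on in-person shopping for Control was softened because of the pandemic, so the split by receipt type may be less than complete. It does not close the gap. Double entry catches keying errors, but not a rule or expectation shared by two unmasked people. Collecting receipts the same way does not remove the account access that staff have for the online arms only.

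A reader might infer four stronger things that the documents do not support:
- That the coders are the same people who allocate and fill carts. Only study staff in general are named, and the roles may be separate. A separate coder would still see the receipt type in the intervention weeks, but need not know more.
- That gaps do depend on receipt type. This is plausible but nowhere stated.
- That the post-test comparison is biased by design. Shopping mode is free in that week.
- That DASH scores are distorted by nutrient substitution. They are built from food amounts.

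**Conclusion.** The point holds in limited form, as a cheap improvement. The plan describes no masking of receipt coding and no record of USDA substitutions. Differential error between Control and the online arms therefore cannot be excluded in the intervention-period, overall and change contrasts. Section 3.0 gives the first of these weight by placing the whole study period within the primary analyses. At post-test the receipt-type route is weak, and it does not touch Online versus Defaults in the intervention weeks. Coder expectation remains possible throughout.

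The size cannot be derived from the documents. The 0 to 0.225 SD range for the intervention weeks rests wholly on assumed gap rates, a one-directional error in standard values, an assumed CV and complete separation of receipt types. If any of the first two is absent, the shift is zero. The figure should not be set directly against d = 0.44, which the plan takes from a post-test difference in the earlier study. On the same assumptions the post-test shift is at most about 0.11 SD for a 50-point difference in online share.

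**What to change.** Amend Sections 12.2 and 19.3 as follows.

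1. Identify each item from the receipt and the receipt form under one written rule for all receipt types. Do not use Instacart account look-up, since nothing equivalent exists for Control.
2. Pool the distinct products from all arms and weeks into one table without participant, arm or date.
3. Code each product once in the nutrition software, with one stated definition of missing information and one substitution rule. Merge the codes back to receipts by program.
4. Flag substituted items and report their share by arm and week.
5. Run one sensitivity analysis that applies standard values to the flagged product types in all arms.

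This needs no new data and uses the same staff and software. Receipts already entered must be mapped to the table once; the revision history for version 11 shows that entry had begun. Giving up account look-up may lose some product detail in the online arms. Masking is only partial: item text may still hint at the receipt type, and the identification in item 1 still requires someone to read the receipt, which is why it needs its own rule.
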